11.3 Planned Interim Analyses (if applicable)

There are no planned interim analyses or safety reviews for this trial.

11.4 Final Analysis Plan

Primary analysis: To compare the ganciclovir pharmacokinetics and pharmacodynamics as measured by AUC₁₂ in premature infants with postnatally or congenitally acquired CMV infection differ from those in term neonates and older infants, we will construct 95% confidence intervals around the mean AUC₁₂ for the subjects in this study and compare these means across the groups. If there are not enough subjects in the groups, we will use the actual gestational age and correlate it with the AUC₁₂ by computing correlation coefficients and a fitting regression model. Additional pharmacokinetic parameters that compose analyses for secondary endpoints include Cmax, T1/2, CL, and VD. For measures that are repeated over time, we will utilize mixed models for repeated measures. In addition to being able to compare these outcomes for the different groups, we can also look into how these measures change over time and adjust for covariates.

Ganciclovir pharmacokinetic parameters will initially be determined using non-compartmental analysis (WinNonlin v5.3) for each individual subject. The parameters (AUC₁₂, CL, Vd, etc.) will be summarized and further used for exploratory pharmacodynamic analysis. We will also apply pharmacokinetic models to the concentration-time data, either individually or using a population approach. We may also pool these data with prior CASG 109 PK data in order to have a more robust covariate analysis across a wider range of ages.

The second pharmacokinetic analysis will utilize either population pharmacokinetic or individual modeling approaches, depending upon how much data we actually are able to collect and the nature of those data. Concentration-time data will be analyzed using nonlinear mixed-effects in ADAPT 5.0. If a population approach is employed, this will give us the opportunity to explore

relationships between ganciclovir exposure and multiple covariates, such as gestational age, weight, renal function, etc.

A 95% confidence interval will be constructed to evaluate the mean changes in the log of the viral load between baseline (day 1) and weeks 1, 2, 3, 4, 5, and 6. Area under the curve will be calculated for each subject's CMV viral load measurement utilizing the trapezoidal rule. These AUCs will be calculated over the entire course of drug administration. Spearman's correlations will be given for each AUC estimation and also for the AUC after baseline viral load (VL) adjustment. Analysis of variance will be used to investigate whether grouping AUCs into groups (undetected, 100-1000, 1000-10000 and ≥ 10000) would indicate any PD relationships. In addition, changes in CMV viral load from baseline over time (weeks 1 through 6) will be correlated with PK parameters. These data will provide the framework for all PD analyses, where ganciclovir exposures variables will be correlated with the response variables using linear or maximum effect PD models.

Secondary analyses: To investigate the association of secondary outcomes namely, neutropenia, CMV in urine, viral load and resistance to ganciclovir, with plasma concentration, we will utilize inference methods based on Generalized Estimating Equations (GEE) which models repeated binary data. As in the primary analysis, GEE will enable us to compare groups, investigate changes of outcomes over time, and adjust for any covariates.

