11 STATISTICAL CONSIDERATIONS

11.1 Study Hypotheses

Our primary hypothesis is that ganciclovir pharmacokinetics and pharmacodynamics in premature infants with postnatally or congenitally acquired CMV infection differ from those in term neonates and older infants.

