11.2 Sample Size Considerations

The primary outcome used for power analysis is the area under the curve for 12 hours (AUC12) following 6 mg/kg of ganciclovir. In a one-way ANOVA design, we would like to compare the means of 4 groups (see below) with sample sizes of approximately 8, 8, 8, and 8 (32 total subjects enrolled across the four cohorts). If the means of the AUC12 of the 4 groups are 20, 20, 30, and 35 assuming a common standard deviation of 10, these mean differences (equivalent to an effect size of 0.72) will be detected at 83% power using an F test with 0.05 level of significance. In order to look at other possible scenarios, we provide the table below that looks at other standard deviation values, its corresponding effect size given the differences in means as described above, and the power of detecting such a difference/effect size. If estimating the AUC without regard to the groups, the margin of errors associated with a 95% confidence interval assuming different standard deviation values and a sample size of 32 are given in the table below.

Standard Deviation	S=8	S=9	S=10	S=11
Effect Size	0.81	0.72	0.64	0.59
Power	96%	91%	83%	75%
Margin of Error	2.33	2.62	2.91	3.20

The above parameter values were hypothesized based on results from other studies.^{25,34} It is worth noting that there are no PK data in this population and the results are likely to be different from other studies due to the maturational changes.

Following enrollment, subjects will be stratified by gestational age and by chronologic age as follows: 1) \leq 27 weeks 6 days gestational age at birth and \leq 30 days chronologic age at study enrollment; 2) \leq 27 weeks 6 days gestational age at birth and $>$ 30 days chronologic age at study enrollment; 3) \geq 28 weeks 0 days gestational age at birth and \leq 30 days chronologic age at study enrollment; 4) \geq 28 weeks 0 days gestational age at birth and $>$ 30 days chronologic age at study enrollment. The total sample size across these four cohorts is 32 subjects. Enrollment of an additional 2-3 subjects may be allowed for operational reasons. If the 32

subjects enrolled are not balanced across the 4 groups, we instead will look at the correlation between gestational age at birth. With 32 subjects, the margin of errors of a 95% confidence interval for estimating the correlation given the observed correlation values are given below.

Correlation	0.4	0.5	0.6	0.7
Margin of Error	0.6	0.542	0.47	0.38

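### The primary hypothesis compares premature with term and older infants, but no comparator or test is assigned to it; the power and planned comparison lie within four premature cohorts, and three figures in section 11.2 need correction

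*Protocol*

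**What the plan says.** **Hypothesis.** Protocol 11.1 and SAP Appendix B state that pharmacokinetics and pharmacodynamics in premature infants "differ from those in term neonates and older infants". Both documents repeat this as the aim of the primary AUC12 analysis.

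**Population.** Protocol 5.1 admits only infants born before 32 weeks, and 14.4 confirms that only premature infants are studied.

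**Power.** Protocol 11.2: "In a one-way ANOVA design, we would like to compare the means of 4 groups". The groups are the four gestational-age by chronologic-age cohorts, about 8 infants each. The outcome is the "area under the curve for 12 hours (AUC12) following 6 mg/kg of ganciclovir", although section 4 leaves dose to the treating physician. The text describes the planning differences at SD 10 as "equivalent to an effect size of 0.72) will be detected at 83% power".

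**Primary method.** Protocol 11.4 uses 95% intervals around mean AUC12 "for the subjects in this study and compare these means across the groups", with correlation and regression on gestational age if the groups are too small. It adds: "For measures that are repeated over time, we will utilize mixed models for repeated measures". SAP Appendix B makes mixed models for repeated measures the primary AUC12 analysis and gives neither the intervals nor the fallback.

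**External data.** Both documents say: "We may also pool these data with prior CASG 109 PK data in order to have a more robust covariate analysis". Protocol 2.1 reports AUC12 from two earlier neonatal studies as background and names neither as comparator.

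**Precision.** Protocol 11.2 continues: "If estimating the AUC without regard to the groups, the margin of errors associated with a 95% confidence interval", and prints 2.33, 2.62, 2.91 and 3.20 for SD 8, 9, 10 and 11. A second table gives margins for a correlation. The SAP prints neither set of margins.

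**The concern.** The hypothesis asks whether premature infants differ from another population. The planned comparison asks whether four kinds of premature infant differ from each other. A reader who sees 83% power beside the hypothesis may take it as power for the hypothesis, which it is not.

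If the hypothesis is addressed at all, someone must choose a reference after the data are in: a published mean, a published median or the optional pooled data. They must also decide whether that reference is a fixed number or an estimate with its own error. Neither choice is pre-specified, and either can change the conclusion.

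Two documents with two primary methods add a further choice. If the study is read as estimation instead, section 11.2 promises more precision for the mean than a 95% interval will deliver.

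**Working it through.** **1. Reproduce the power (Protocol 11.2).** Planning means are 20, 20, 30, 35; overall mean 26.25; SD of the four means (divisor 4) 6.495. Effect size f = 6.495/SD; noncentrality 32f²; F test on 3 and 28 df at 0.05.

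| SD | f computed (table) | power computed (printed) |
|---|---|---|
| 8 | 0.812 (0.81) | 96.2% (96%) |
| 9 | 0.722 (0.72) | 90.6% (91%) |
| 10 | 0.650 (0.64) | 83.1% (83%) |
| 11 | 0.590 (0.59) | 74.7% (75%) |

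The power row reproduces, so the 83% is a contrast among premature cohorts. The text's 0.72 belongs to SD 9; taken literally it would give 90.5% power. At SD 10 the value is 0.65.

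**2. The F test and the hypothesis.** If all four cohorts share one mean, however far from term, noncentrality is 0 and rejection equals the 5% test level.

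**3. What an improvised external comparison would show (illustration only).** Take the premature mean as 26.25, SD 10, n = 32, in the units of section 2.1. Standard error = 10/√32 = 1.768; 95% interval 26.25 ± 3.61 = 22.6 to 29.9.

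- Published mean 32.3 as a fixed value: t = 6.05/1.768 = 3.42, p = 0.002.
- The same mean as an estimate (n = 13; the printed 13.7 assumed to be an SD): SE = √(100/32 + 13.7²/13) = 4.19, 17.4 df; difference 6.05, 95% CI −2.8 to 14.9, p = 0.17.
- Published medians 27 or 25.5 as fixed values: each is 0.75 from 26.25, t = 0.75/1.768 = 0.42, p about 0.67.

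The contrast between the first two persists at the ungrouped SD implied by the planning means, √(100 + 6.495²) = 11.9 (p = 0.007 against 0.18), and at SD 13.7 (0.018 against 0.19).

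**4. Margins for the mean.** Formula: multiplier × SD/√32.

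| SD | printed | 1.645 (90%) | 1.960 (95%, z) | 2.040 (95%, t, 31 df) |
|---|---|---|---|---|
| 8 | 2.33 | 2.33 | 2.77 | 2.88 |
| 9 | 2.62 | 2.62 | 3.12 | 3.24 |
| 10 | 2.91 | 2.91 | 3.46 | 3.61 |
| 11 | 3.20 | 3.20 | 3.81 | 3.97 |

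The printed row matches the 90% multiplier. True 95% margins are 19% wider by z (1.960/1.645) or 24% wider by t (2.040/1.645).

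**5. Margins for the correlation.** Fisher interval, tanh(atanh r ± 1.96/√29).

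| r | printed margin | full 95% width | half-width |
|---|---|---|---|
| 0.4 | 0.6 | 0.597 | 0.299 |
| 0.5 | 0.542 | 0.539 | 0.270 |
| 0.6 | 0.47 | 0.467 | 0.233 |
| 0.7 | 0.38 | 0.378 | 0.189 |

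These are at the stated 95% level, but they are full widths (to within 0.003) presented as margins.

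**6. Protocol and SAP methods.** With one AUC12 per infant and cohort as the only factor, a mixed model reduces to the one-way ANOVA. The two can part only through covariates or through second profiles. Under section 4 a second profile is optional, physician-requested and taken in Period 4; the site is sent the first AUC and clearance for information. Neither document specifies the model, so the difference cannot be sized.

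**The case against.** The strongest reply is that the primary objective in Protocol 3.1 is descriptive: to define ganciclovir pharmacokinetics in premature infants. Overall and cohort means with 95% intervals deliver that. On this view the hypothesis is misworded and the study is sound. That largely stands, and it limits the severity.

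Four stronger readings might be inferred, and the documents do not support them:

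- *That the F test carries no information on the hypothesis.* If cohort means differ, they cannot all equal one common term mean, so a significant result implies that at least one differs from it. The test is indirect: it does not say which cohort, and it is blind to an equal shift.
- *That only the method of comparison matters, not the reference.* The means in section 2.1 (32.3 and 38.2) lie outside the 22.6 to 29.9 interval, but the medians beside them (27 and 25.5) lie inside. Both choices matter.
- *That the two primary methods will give conflicting results.* No such consequence can be shown. The clear differences are the unspecified model and the SAP's missing fallback.
- *That free dosing invalidates the cohort comparison.* Raw AUC12 can reflect prescribed dose, but the documents give no size for any dose difference between cohorts. Clearance, which accounts for dose, is already a secondary endpoint, and covariate modelling is foreseen if a population approach is used.

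It is also fair that the external p-values are only illustrations. They use planning means and normal theory. The study behind 38.2 reports a coefficient of variation of 112, which points to skew. The reference cited for 32.3 is titled as single-dose work, whereas this study samples doses 3 to 8.

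**Conclusion.** The plan is wrong as written and should be fixed. Its stated primary hypothesis has no comparator, reference value or test. Optional pooling for covariate analysis does not supply one. The 83% power is correct for a different question. With the reference and method left open, the illustrative p-value ranges from 0.002 to about 0.67 on the same assumed data (mean 26.25, SD 10, n = 32; 13.7 read as an SD where the comparator's error is counted).

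The protocol and SAP need one primary method, although with one profile per infant and no covariates the two named methods coincide. In 11.2, the mean margins are 90% rather than 95%, the text effect size at SD 10 is wrong while the power stands, and the correlation margins are twice the half-width. The last three points are corrections to printed figures and do not alter an analysis.

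**What to change.** **(a) Hypothesis.** Reword Protocol 11.1, the opening of 11.4 and SAP Appendix B: estimate AUC12 in infants born before 32 weeks and compare it across the four cohorts; any comparison with term or older infants is descriptive and non-concurrent. Alternatively, pre-specify a comparator dataset that the sponsor confirms is suitable, with a 95% interval that includes the comparator's own uncertainty.

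**(b) One primary text in both documents.** One AUC12 per infant from the first profile; overall and cohort means with 95% intervals; one-way ANOVA F test at 0.05. Keep the protocol's gestational-age correlation and regression as the fallback for imbalanced cohorts. Make Period 4 profiles secondary. Report AUC12 normalised to the 6 mg/kg used in planning, or clearance per kg, alongside as a supportive analysis. This concerns analysis only, not dosing.

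**(c) Figures.** Give the effect size at SD 10 as 0.65 in Protocol 11.2 and SAP Appendix B, text and table; power stays 83%. In Protocol 11.2 print 95% margins of 2.88, 3.24, 3.61 and 3.97 for SD 8, 9, 10 and 11 (t; by z 2.77, 3.12, 3.46 and 3.81). Relabel the correlation row as full 95% interval widths, or print half-widths of about 0.30, 0.27, 0.23 and 0.19.

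**Cost.** Text and figures only, with no change in sample size or procedures. Dose, interval and weight are already recorded on the sampling day. Only the alternative in (a) needs a further step: sponsor confirmation of a dataset.

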The appropriate dose of intravenous ganciclovir for premature babies has not been studied. Previous studies of ganciclovir have indicated that the area-under-the-concentration curve (AUC) of ganciclovir is most closely related to virologic treatment success.²³ Data from an National Institute of Allergy and Infectious Diseases (NIAID) CASG Phase II study of intravenous ganciclovir (6 mg/kg/dose q 12 hrs) in term neonates with symptomatic congenital CMV disease revealed a median AUC₁₂ of 27 μ gxh/mL (mean AUC₁₂=32.3+13.7 μ gxh/mL, range 17.2 to 55.9 μ gxh/mL, n=13).²⁴ A more recent CASG investigation of oral valganciclovir included comparative pharmacokinetic data following 6 mg/kg/dose every 12 hrs of intravenous ganciclovir. The mean AUC₁₂ in young neonates (median age: 16.5 days) on the second day following study enrollment was 38.2 μ gxh/mL (median: 25.5 μ gxh/mL), but the coefficient of variation was large (112).²⁵ In five neonates in whom pharmacokinetic sampling was performed on day 4 and day 34 of intravenous ganciclovir therapy, ganciclovir clearance nearly doubled and AUC₁₂ reduced by almost half over the 30 day interval,²⁵ suggesting that maturational changes may be occurring rapidly in early life which may affect ganciclovir dosing. No data exist on ganciclovir dosing in very premature babies, who are at greatest risk for CMV disease.

due to the absence of transplacental antibodies. Notably, acyclovir must be dose-adjusted based upon renal function such as that which can occur with prematurity.²⁶

The CASG and the UAB Central Unit have had significant success in performing multi-center pharmacokinetic and pharmacodynamic studies with both ganciclovir and valganciclovir in infants during the first month of life.^{21,22,25,27-30} In this study, this experience will be utilized to further define the utility of this drug in very premature children.

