With the receipt of one of the Study Assessment Doses (dose 3, 4, 5, 6, 7, or 8) of intravenous ganciclovir, pharmacokinetic specimens will be obtained at 0h (immediately prior to IV ganciclovir dose; window: -15 min), 1h (immediately after the end of the IV ganciclovir dose; window: +15 min), 2-3h, 5-7h, and 10-12h. This complete set of pharmacokinetic time points will allow for the AUC and clearance (CL) to be calculated in each subject. Specimens will be shipped to the UAB Antiviral Pharmacology Laboratory for processing at that time. The pharmacokinetic data will then be provided to the study site, including the AUC and CL values,

for information purposes. The decision of whether or not to adjust the dose will be a clinical one to be decided by the treating physician, and will not be dictated by the research protocol. The parameters for AUC and CL from prior CASG ganciclovir^{27,30} and valganciclovir^{25,29} studies demonstrate that these PK parameters may be useful in guiding dose adjustments. Duration and dose of intravenous ganciclovir therapy is made at the discretion of the treating physician and will not be dictated by the research protocol.

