Both whole blood for CMV PCR and urine for CMV assessment will be obtained serially through Study Assessment Period 7 as long as the subject is receiving intravenous ganciclovir therapy (that is, until the ganciclovir is permanently discontinued). These specimens will be used to determine viral load and, as indicated, ganciclovir resistance. At each sample collection time, urine will be split into two aliquots. These aliquots will be available for CMV detection as appropriate, based upon whole blood viral loads. Specimens will then be available for subsequent testing for ganciclovir resistance in the UAB Virology Resistance Laboratory. Since ganciclovir is a renally excreted drug, serum creatinine will be drawn for the research protocol on the day that the ganciclovir pharmacokinetic specimens are obtained in order to calculate creatinine clearance using a method such as the modified Schwartz formula, and thus correlate ganciclovir clearance with renal function. Otherwise, data from hematology assessments (WBC count and differential, hemoglobin, platelet count) and from chemistry labs (serum creatinine, ALT, and AST) will be recorded on the study case report forms each study assessment period if they are being obtained for clinical reasons, but will not be drawn only for the purposes of the study. Ganciclovir dosing information (mg/dose, dosing interval, and subject weight) will be recorded on the day of the pharmacokinetic blood draws. Once a subject is successfully enrolled into the study the ganciclovir dosing information (mg/dose and dosing interval) will be recorded from the start of clinical treatment of ganciclovir until date of enrollment. After enrollment ganciclovir dosing information (mg/dose and dosing interval) will be captured from Study Assessment Period 1 through the Study Assessment Period 7; as long as the subject is receiving intravenous ganciclovir therapy.

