5.1 Subject Inclusion Criteria

1. Signed informed consent from parent(s) or legal guardian(s)
2. Confirmation of CMV infection from urine, blood, or saliva by culture, shell vial, or PCR tests (local lab)
3. Receiving intravenous ganciclovir, prescribed by the patient's physician and anticipated to receive at least 3 more doses after consenting
4. < 32 weeks gestational age at birth
5. ≥ 500 grams at study enrollment

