Primary analysis: To compare the ganciclovir pharmacokinetics and pharmacodynamics as measured by AUC12 in premature infants with postnatally or congenitally acquired CMV infection differ from those in term neonates and older infants, we will utilize mixed models for repeated measures. Additional pharmacokinetic parameters that compose analyses for secondary endpoints include Cmax, T1/2, CL, and VD. In addition to being able to compare these outcomes

for the different groups, we can also look into how these measures change over time and adjust for covariates.

Ganciclovir pharmacokinetic parameters will initially be determined using non-compartmental analysis (WinNonlin v5.3) for each individual subject. The parameters (AUC₁₂, CL, Vd, etc.) will be summarized and further used for exploratory pharmacodynamic analysis. We will also apply pharmacokinetic models to the concentration-time data, either individually or using a population approach. We may also pool these data with prior CASG 109 PK data in order to have a more robust covariate analysis across a wider range of ages.

The second pharmacokinetic analysis will utilize either population pharmacokinetic or individual modeling approaches, depending upon how much data we actually are able to collect and the nature of those data. Concentration-time data will be analyzed using nonlinear mixed-effects in ADAPT 5.0. If a population approach is employed, this will give us the opportunity to explore relationships between ganciclovir exposure and multiple covariates, such as gestational age, weight, renal function, etc.

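### The primary comparison of AUC12 across cohorts is not scaled to dose, although dose is the physician's choice and the study is powered at 6 mg/kg

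*Protocol*

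**What the plan says.** The primary hypothesis (Protocol 11.1, repeated in SAP Appendix B) is about a difference in pharmacokinetics. The primary endpoint is AUC12 (Protocol Summary and 3.2.1).

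- **Sample size.** Protocol 11.2: "The primary outcome used for power analysis is the area under the curve for 12 hours (AUC12) following 6 mg/kg of ganciclovir". It assumes cohort means of 20, 20, 30 and 35, a common SD of 10 and 8 infants per cohort, and gives 83% power for an F test at 0.05.
- **Primary analysis.** Protocol 11.4 constructs 95% confidence intervals around mean AUC12 "for the subjects in this study and compare these means across the groups". If cohorts are too small, AUC12 is correlated with gestational age. For the same comparison SAP Appendix B says "we will utilize mixed models for repeated measures". Neither text divides by dose or restricts the analysis to one dose.
- **Dose.** Protocol section 4: "Duration and dose of intravenous ganciclovir therapy is made at the discretion of the treating physician". The inclusion criterion on ganciclovir sets no mg/kg: "Receiving intravenous ganciclovir, prescribed by the patient's physician and anticipated to receive at least 3 more doses after consenting".
- **Recorded data.** Protocol section 4: "Ganciclovir dosing information (mg/dose, dosing interval, and subject weight) will be recorded on the day of the pharmacokinetic blood draws".
- **Other analyses.** CL is a secondary endpoint. Individual or population pharmacokinetic modelling is planned as a further analysis. On the group comparison, 11.4 adds that "we can also look into how these measures change over time and adjust for covariates".

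**The concern.** With linear kinetics at steady state, the AUC over a dosing interval equals dose divided by clearance. AUC12 therefore measures the infant's handling of the drug only when dose is held constant. Section 11.2 keeps that condition and the analysis sections drop it. The term-neonate AUC12 values in Protocol 2.1 are also at 6 mg/kg every 12 hours, so unscaled AUC12 at other doses cannot be set beside them.

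A systematic dose difference is plausible, though not documented. Section 2.1 says that the dose for premature babies has not been studied and that the dose of acyclovir must be adjusted for renal function. The cohorts are defined by maturity. If prescribing followed maturity, the primary comparison would mix prescribing with clearance. A primary result on AUC12 could then point one way and the secondary result on CL another, and the plan does not say which one answers the hypothesis.

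**Working it through.** **Inputs.** From 11.2: means 20, 20, 30, 35; SD 10; n = 8 per cohort; F test at 0.05. From 2.1: SD 13.7 for AUC12 in 13 term neonates at 6 mg/kg every 12 hours. Cohort doses are assumptions, because the documents give none. Section 11.4 names no test, so the F test of 11.2 is used.

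**Formula.** One-way ANOVA with 4 groups, df 3 and 28. Noncentrality λ = 8 × Σ(mᵢ − m̄)² / SD². The rejection probability comes from the noncentral F distribution.

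**1. The plan's own figure.** m̄ = 26.25. The squared deviations are 39.06, 39.06, 14.06 and 76.56, which sum to 168.75. λ = 8 × 168.75 / 100 = 13.5, giving power 0.831. The stated 83% is reproduced.

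**2. Equal clearance, unequal dose.** Let AUC12 be 30 at 6 mg/kg in every cohort. Two cohorts receive d mg/kg and so have mean 30 × d/6. SD is held constant.

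| Dose in two cohorts | Means | Σ(mᵢ − m̄)² | λ, SD 10 | P(reject), SD 10 | λ, SD 13.7 | P(reject), SD 13.7 |
|---|---|---|---|---|---|---|
| 6 mg/kg | 30, 30, 30, 30 | 0 | 0 | 5% | 0 | 5% |
| 5 mg/kg | 25, 25, 30, 30 | 25 | 2.0 | 17% | 1.07 | 11% |
| 4 mg/kg | 20, 20, 30, 30 | 100 | 8.0 | 59% | 4.26 | 33% |

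If the SD shrinks in proportion to dose instead of staying at 10, simulation gives 20% and 74% for 5 and 4 mg/kg. The planned contrast of 20 against 30 is what 4 against 6 mg/kg produces with identical clearance (4/6 = 20/30).

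**3. Equal mean dose, dose varying between infants.** There is then no bias, only extra variance. Take m = 26.25 and CV₀ = 10/26.25 = 0.381, with dose independent of clearance. SD = m × √[(1 + CV₀²)(1 + CV_dose²) − 1]. For a dose CV of 20%, SD = 26.25 × √(1.1451 × 1.04 − 1) = 11.47. Then λ = 1350 / 11.47² = 10.26 (1350 = 8 × 168.75) and power is 0.707. Dose CVs of 10% and 30% give 80% and 58%.

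**4. After normalisation.** In a lognormal simulation with AUC12 scaled to 6 mg/kg, rejection is 4% to 5% under equal clearance and 82% to 83% under the planned difference, whatever the cohort doses. This follows by construction from linear kinetics.

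**The case against.** The strongest reply is that dose-free pharmacokinetics will be delivered anyway. CL is a prespecified endpoint, 11.4 intends group comparisons of these parameters, and it commits to pharmacokinetic modelling, in which dose is an input. This stands as a limit on scope: the gap is in the primary comparison and not in the whole analysis. It does not close the gap, because CL is secondary and nothing makes it govern.

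AUC12 also has a rationale of its own. Section 2.1 says AUC is the measure most closely tied to virologic success, so achieved exposure deserves reporting. That supports keeping observed AUC12, but not using it to test whether pharmacokinetics differ.

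Several stronger readings are tempting and are not supported:

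- **That a true difference would be masked.** If the cohorts with means 30 and 35 received 5 or 4 mg/kg, power would fall to 37% or 9%. But 11.2 does not say which cohort has which mean. If the means follow the listed order, lower doses for the most immature infants lower the means of 20 and raise rejection, to 91% at 5.5 mg/kg and 96% at 5 mg/kg. The direction of distortion is unknown.
- **That dose was deliberately left out of adjustment.** The listed covariates belong to the population model, where dose enters anyway. The sentence on group comparison names no covariates at all. It is permissive, and so neither provides nor excludes adjustment for dose.
- **That the interval is also at the physician's discretion.** The protocol says this of dose and duration only. It describes twice-daily dosing as typical.
- **That repeat profiles will hide maturation.** Section 2.1 reports that "ganciclovir clearance nearly doubled" over 30 days, but in five neonates. The second profile here is optional and needs a weight of at least 575 g. A dose change between profiles could offset a clearance change, but how often is unknown.

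**Conclusion.** The point holds for the primary comparison, its gestational-age fallback and the SAP mixed model. As written, they test a pharmacokinetic hypothesis on a variable that also carries the prescribed dose. The change should be made.

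The size is conditional. With the assumed 5 or 4 mg/kg in two cohorts and equal clearance, false rejection is 17% or 59% at SD 10 and 11% or about 33% at SD 13.7. With equal mean doses the cost is power only: 83% to about 71% at an assumed dose CV of 20%. With 6 mg/kg for all there is no effect. The figures assume linear kinetics and, in the bias case, a systematic difference in mg/kg between cohorts. A reader might infer that the primary result will be biased. The documents show only that it could be, since they contain no data on the doses given.

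**What to change.** In Protocol 11.4 and SAP Appendix B, define the primary variable as AUC12 normalised to 6 mg/kg: 6 × AUC12 / actual mg/kg on the PK day. At steady state on 12-hourly dosing this equals 6 divided by CL per kg, so CL per kg carries the same information; name one of the two in advance. Use it in the cohort comparison, the gestational-age fallback and the mixed model. Amend the primary endpoint wording in the Protocol Summary and 3.2.1 to match.

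Report observed AUC12 by cohort, beside mg/kg and dosing interval, as achieved exposure. For any infant not dosed every 12 hours, take CL from the AUC over the actual interval. Intervals longer than 12 hours need extrapolation, because sampling ends at 10 to 12 hours. Flag infants whose dose changed shortly before sampling, since the PK-day dose may then not match the exposure.

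**Cost.** Rewording of the two analysis sections and the endpoint statements. No extra blood, infants or data are needed, because mg/dose, interval and weight are already recorded on the PK day. The downside is that normalisation assumes linear kinetics over the doses used and approximate steady state, and sampling may be as early as the third dose after enrolment.
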